8.1.1.4 Unanesthetized Schirmer Tear Test (STT)

Schirmer Tear Test (without anesthesia) will be conducted at Visit 1, Visit 4 and Visit 5. This procedure should be conducted at least 1 hour following administration of IP and at least 20 minutes following FCS at Visit 4 and Visit 5:

Identical Schirmer strips will be supplied to each site. When conducting assessments room temperature and humidity should be relatively consistent throughout each visit and throughout the study.

- While still in the plastic sheath, fold the notched end of the Schirmer strip at the apex of the “v.” Additionally, make a partial second fold at the halfway point of the strip so that the strip does not lie directly in the subject’s line of sight
- Remove the right eye strip from the sheath
- Ask the subject to look up and gently draw the right lower lid in a downward and temporal direction

- Place the rounded end of the strip toward the temporal one-third of the lower eyelid
- Repeat this procedure in the left eye
- Darken the room but ensure that the largest letter(s) of a Snellen or ETDRS chart is visible
- Instruct the subject to relax and look at the chart while blinking normally or have patients gently close eyes
- Remove the strips after 5 minutes
- After removing the strips, with a sharp pencil draw a horizontal line across the leading edge of moisture and a second horizontal line across the lowest point of moisture
- Using a ruler and/or the millimeters recorded on the strips, measure a point halfway between the two lines and record this as the amount of wetting

8.1.2 Post-Instillation Tolerability Assessments

8.1.2.1 Drop Discomfort Assessment

Drop discomfort will be assessed by the subject through a Drop Discomfort VAS (0-100 mm) where 0 corresponds to “no discomfort” and 100 corresponds to “maximal discomfort.” (See [Appendix 1](#)).

At Visit 2, prior to randomization, in order to evaluate the subject’s ability to tolerate ocular drops, all subjects will self-administer an OTC ocular lubricant, Refresh Plus[®], OU. Upon instillation of the ocular lubricant OU, subjects will be instructed by the site staff to rate their eye discomfort at 1-minute and 5-minutes post-instillation by placing a mark on the Discomfort VAS. Subjects who rate OTC ocular lubricant as uncomfortable, defined as a VAS score ≥ 30 mm, will not be eligible for participation in the study. These Drop Discomfort VAS scores will be used as the baseline values.

At Visit 2, after randomization, an unmasked dedicated dosing coordinator will instill the IP OU. Subjects will be instructed by a masked site staff to rate their eye discomfort at 1-minute and 5-minutes post-instillation of IP as described above.

Subjects will complete this assessment in the clinic following the AM dose of IP at Visits 2, 3, 4 and 5 and again at home following the PM dose on the evenings of Visits 2, 3, 4 and the evening prior to Visit 5.

8.1.3 Safety Assessments

The following assessments will occur as part of the safety evaluation of the subjects:

8.1.3.1 Best Corrected Visual Acuity (BCVA)

BCVA will be conducted at each visit per the Schedule of Events. Visit 1 BCVA will be used to assess eligibility, and Visit 2 BCVA will be used as baseline value. Visual acuity testing should precede any examination requiring contact with the eye or instillation of study dyes. LogMAR visual acuity must be assessed using an ETDRS or modified ETDRS chart. Visual acuity testing should be performed with best correction using subject's own corrective lenses (spectacles only) or pinhole refraction.

An ETDRS or modified ETDRS chart may be used, and charts may be reflectance or retro-illuminated. If a 24.5" by 25" chart is used, the subject must view the chart from exactly 4 meters (13.1 feet). If smaller reproductions (18" by 18", e.g., Prevent Blindness) are used, the subject viewing distance should be exactly 10 feet. Reflectance wall charts should be frontally illuminated (60-watt bulb or a well-lit room).

The subject should be positioned per the elevation of the chart (either seated or standing) so that the chart is at a comfortable viewing angle. The right eye should be tested first. The subject should attempt to read each letter, line-by-line, left to right, beginning with line 1 at the top of the chart. The subject should be told that the chart has letters only, no numbers. If the subject reads a number, he or she should be reminded that the chart contains no numbers, and the examiner should then request a letter instead of the number. The subject should be asked to read slowly, about 1 letter per second, to achieve the best identification of each letter. He/she is not to proceed to the next letter until he/she has given a definite response. If the subject changes a response before he has read aloud the next letter, then the change must be accepted.

Maximum effort should be made to identify each letter on the chart encouraging the subject to guess. When it becomes evident that no further meaningful readings can be made, the examiner should stop the test. The number of letters missed or read incorrectly should be noted (see [Appendix 6](#)).

8.1.3.2 Dilated Ophthalmoscopy

Dilated ophthalmoscopy exam will be performed per the Investigator's standard procedure at Visit 1 and Visit 6.

The Investigator will determine if findings are within normal limits or are abnormal. For abnormal findings at Visit 1, the Investigator will determine whether the abnormality would exclude subject from study participation. A clinically significant change from baseline may indicate an AE.

8.1.3.3 Slit-Lamp Biomicroscopy

The biomicroscopy exam will be performed at Visit 2 and Visit 5. It should be performed with the Slit-Lamp using a beam of width and intensity to provide optimal evaluation of anterior segment.

This procedure will be performed in the same manner for all subjects observed at the Investigator's site (see [Appendix 5](#)).

8.2 Schedule of Assessments

A detailed schedule of assessments (including all protocol-required assessments, visits, and visit windows) is located on the Schedule of Events ([Table 1](#)). No study-related assessments will be performed (including changes to current medications to meet study eligibility) until the subject has provided signed and dated informed consent. Every effort will be made to keep the subject within the requested visit schedule. If a subject is seen outside of the visit window listed on the Schedule of Events, the reason must be clearly documented in the source notes.

8.2.1 Screening Procedures

8.2.1.1 VISIT 1

The screening visit will take place within 3 days prior to Visit 2. After obtaining informed consent, site staff will perform/assess the following procedures in the order below. There will be a collection of information including:

- Demographics
- Prior documented DED diagnosis
- Ocular, general medical and surgical history
- Concomitant medication history
- UPT for all eligible WOCBP
- BCVA assessment
- Unanesthetized STT
- Dilated Ophthalmoscopy
- Assessment of ocular lubricant self-instillation
- AE assessment

- Inclusion and exclusion criteria assessment: Subjects who do not meet the evaluated criteria will not continue participation in the study. Any subject who does not meet eligibility requirements will be considered a Screen Failure.

Subjects should be reminded not to use artificial tears or any other OTC or prescription or any other topical eye medication except for the IP for the duration of their participation in the study.

Subject will be scheduled to return for Visit 2 in one to three days.

8.2.2 Treatment Procedures

8.2.2.1 VISIT 2

Pre-Randomization

The site staff will perform/assess the following procedures:

- SANDE
- Individual Symptom Severity Assessments (VAS)
- AE assessment
- Concomitant medication review
- BCVA assessment
- Self-instillation of ocular lubricant and Drop Discomfort assessment (VAS)
- Slit-Lamp biomicroscopy
- FCS
- Inclusion and exclusion criteria assessment. Any subject who does not meet eligibility requirements will be designated as Visit 2 Screen Failure and discontinued from the study

Upon verification of study eligibility, subjects will be randomized to receive either VOS or Restasis®.

Post-Randomization

The following procedures will be performed after randomization:

- IP administration: the unmasked dedicated dosing coordinator will administer the first dose of IP to the subject OU

Note: IP administration should not take place until at least 2 hours after administration of ocular lubricant.

- Drop Discomfort assessment: A masked site staff will administer the Drop Discomfort VAS to the subject and instruct the subject to complete the Drop Discomfort VAS at 1-minute and 5-minutes post-dose
- Assess for occurrence of any AEs
- IP dispensation: The **unmasked dedicated dosing coordinator** will dispense the IP, provide instructions for IP administration and storage conditions
- Dosing Diary and VAS scales dispensation: Train the subjects on the completion of the daily dosing diary and VAS scales
- Evening contact scheduling: **Masked site staff** will schedule and contact the subject in the evening of the clinic visit to prompt administration of the next dose and completion the Drop Discomfort VAS
- Subjects should be reminded to withhold AM dose of IP on morning of next clinic visit and to return all used and unused IP

Subject will be scheduled to return for Visit 3 on Day 7 \pm 2 days.

PM Contact with Patient:

- **Masked site staff** will call subject to prompt IP administration and will remain on call to facilitate completion of the Drop Discomfort VAS at 1-minute and 5-minutes post-dose

8.2.2.2 VISIT 3 (Treatment Day 7 \pm 2)

The site staff will perform/assess the following procedures:

- SANDE
- Individual Symptom Severity Assessments (VAS)
- AE assessment
- Concomitant medication review
- **Unmasked dedicated dosing coordinator** will collect returned carton containing used and unused IP ampules
- **Unmasked dedicated dosing coordinator** will collect Dosing Diary, Drop Comfort VAS and dispense new Dosing Diary and Drop Comfort VAS

- **Unmasked site staff** will query the subject regarding compliance with dosing and the protocol. If the subject has not been compliant with the dosing regimen, record this in the source document and eCRF and discuss proper compliance with the subject
- BCVA assessment
- IP Administration:
 - The **unmasked dedicated dosing coordinator** will administer the AM dose of IP in the clinic
- Drop Discomfort VAS:
 - The **masked site staff** will administer the Drop Discomfort VAS at 1-minute and 5-minutes post-dose
- Assess for occurrence of any AEs following instillation
- **Unmasked dedicated dosing coordinator** will dispense IP to the subject
- FCS
- Evening contact scheduling: **Masked site staff** will schedule and contact the subject in the evening of the clinic visit to prompt administration of the next dose and completion the Drop Discomfort VAS
- Remind subject to withhold AM dose of IP on morning of next clinic visit and to return all used and unused IP

Schedule the subject to return in 1 week for Visit 4 on Day 14 \pm 2 days.

PM Contact with Patient:

- **Masked site staff** will call subject to prompt IP administration and will remain on call to facilitate completion of the Drop Discomfort VAS at 1-minute and 5-minutes post-dose

8.2.2.3 VISIT 4 (Treatment Day 14 \pm 2)

The site staff will perform/assess the following procedures:

- SANDE
- Individual Symptom Severity Assessments (VAS)
- AE assessment

- Concomitant medication review
- **Unmasked dedicated dosing coordinator** will collect returned carton containing used and unused IP ampules
- **Unmasked dedicated dosing coordinator** will collect Dosing Diary, Drop Comfort VAS and dispense new Dosing Diary and Drop Comfort VAS.
- **Unmasked site staff** will query the subject regarding compliance with dosing and the protocol. If the subject has not been compliant with the dosing regimen, record this in the source document and eCRF and discuss proper compliance with the subject
- BCVA assessment
- IP Administration:
 - The **unmasked dedicated dosing coordinator** will administer the AM dose of IP in the clinic.
- Drop Discomfort VAS:
 - The **masked site staff** will administer the Drop Discomfort VAS at 1-minute and 5-minutes post-dose
- Assess for occurrence of any AEs following instillation
- **Unmasked dedicated dosing coordinator** will dispense IP to the subject
- FCS
- Unanesthetized STT This should be performed no less than 1-hour following the administration of IP and at least 20 minutes following FCS
- Evening contact scheduling: **Masked site staff** will schedule and contact the subject in the evening of the clinic visit to prompt administration of the next dose and completion the Drop Discomfort VAS
- Remind subject to withhold AM dose of IP on morning of next clinic visit and to return all used and unused IP

Schedule the subject to return in 2 weeks for Visit 5 on Day 28 \pm 2 days.

PM Contact with Patient:

- **Masked site staff** will call subject to prompt IP administration and will remain on call to facilitate completion of the Drop Discomfort VAS at 1-minute and 5-minutes post-dose.

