6.2 Masking

On Day 1 Dose 1, this study is double-masked. The IP allocation (VOS versus Restasis®) will be masked to the Sponsor, the subject and the investigative staff with the exception of an unmasked dedicated dosing coordinator and unmasked CRA. The unmasked dedicated dosing

coordinator will be responsible for dispensing and retrieving IP to/from subjects, instructing subjects regarding dosing of the IP, addressing study subjects' questions regarding IP, and reviewing daily dosing diaries. As a consequence of these interactions, the unmasked dedicated dosing coordinator will be unmasked to the study treatment for each subject. In order to ensure subject masking, at Visit 2, first dose, the unmasked dedicated dosing coordinator will not provide any IP related information prior to instilling the IP. The IP will be instilled in a masked manner. Instructions regarding storage and dosing will be provided after this first instillation.

On Days 2-28, subjects will not have visibility to the study product assignment; however, as VOS and Restasis® have different storage conditions and appearance, it may be possible that the subjects who have previously used Restasis®, may know that those differ from their prior experience. Therefore, the study will be considered Investigator-masked during this timeframe.

The randomization schedule will be generated by the Randomization Statistician (who is not on the project team) or designee and maintained in a secure and limited-access location separate from the study Investigator and members of the project team.

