7.5.2 Storage

VOS should be stored refrigerated between 2° C and 8° C (36° F to 46° F) but may be brought to room temperature prior to use. Subjects should be consistent in their use of VOS IP.

Opened ampules must not be stored for re-use as the formulation does not contain preservatives.

STUDY DRUG SHOULD NOT BE FROZEN. DO NOT USE IF THE VIAL CONTENT DOES NOT APPEAR CLEAR.

Restasis® should be stored at room temperature (15-25°C/59-77°F).

Each site should have a thermometer in each storage location that records minimum and maximum temperatures daily. Maintenance of a temperature log is mandatory. The log should be updated by Unmasked site personnel during normal working hours. This log must be available for review by the Unmasked Site Monitor during on-site monitoring visits.

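### The Visit 3 and 4 lists allow IP to be dispensed before masked staining (and, at Visit 4, Schirmer) grading, and the Visit 3-5 lists allow the used carton to stay with the subject through the first AE review: an avoidable masking risk

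*Protocol*

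**What the plan says.** Protocol 8.2.2.2 (Visit 3) and 8.2.2.3 (Visit 4) each contain a step in which the unmasked dosing coordinator "will dispense IP to the subject". FCS is listed after it and, at Visit 4, STT follows FCS. The STT entry adds: "This should be performed no less than 1-hour following the administration of IP and at least 20 minutes following FCS". There is no Schirmer test at Visit 3; under Protocol 8.1.1.4, "Schirmer Tear Test (without anesthesia) will be conducted at Visit 1, Visit 4 and Visit 5".

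At Visits 3, 4 and 5 the coordinator "will collect returned carton containing used and unused IP ampules", but this is listed after SANDE, the symptom VAS, the AE assessment and the medication review.

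Protocol 6.2 concedes that the two products "have different storage conditions and appearance". Protocol 7.1.1 describes VOS as a clear solution, and the package insert in Appendix 8 describes Restasis as a white opaque emulsion. On storage, Protocol 7.5.2 says "VOS should be stored refrigerated between" 2 and 8 °C, whereas Restasis is kept at room temperature. Protocol 6.2 treats the study as double-masked for Dose 1 and as Investigator-masked from then on.

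Protocol 7.3 covers packaging in general terms and does not describe the outer carton.

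**The concern.** After Dose 1, on-site protection against biased assessment rests on keeping the people who assess signs and AEs unaware of the product. FCS is the outcome most open to influence: it is graded by judgement from 0 to 3 in five corneal zones, and it is a key secondary endpoint. STT is also key secondary and, with FCS, feeds the exploratory responder endpoints in SAP 7.5.4. The Investigator also judges AE causality.

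A subject who has just been supplied, or who has not yet handed back the used carton, has the identifying product to hand. There is a spoken route too. Under Protocol 8.2.2.1 the coordinator explains administration and storage after Dose 1, so a subject can mention a refrigerated clear drop without knowing what it is called.

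**Working it through.** **Order of steps as listed (Protocol 8.2.2.2 to 8.2.2.4)**

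| Step, in list order | Visit 3 | Visit 4 | Visit 5 |
|---|---|---|---|
| SANDE, symptom VAS, AE assessment, medication review | yes | yes | yes |
| Used carton returned to coordinator | yes | yes | yes |
| BCVA | yes | yes | yes |
| Slit-lamp | no | no | yes |
| Clinic dose, Drop Discomfort VAS | yes | yes | yes |
| Post-dose AE check | yes | yes | no |
| New IP dispensed | yes | yes | no |
| FCS | yes | yes | yes |
| STT | no | yes | yes |

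If the list is followed:
- the used carton is still with the subject at the first AE assessment at Visits 3, 4 and 5;
- new product is with the subject at FCS at Visits 3 and 4, and at STT at Visit 4;
- neither applies at BCVA, slit-lamp, the post-dose AE check, or FCS and STT at Visit 5.

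**How long at Visit 4.** Dispensing is listed before FCS, and FCS must precede STT by at least 20 minutes. In list order the subject therefore has the product for at least 20 minutes before STT. If dispensing came straight after the 5-minute discomfort rating, and STT at the earliest permitted time of 60 minutes after the dose, the interval would be 60 - 5 = 55 minutes.

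**Is the order binding?** The Visit 1 text says "site staff will perform/assess the following procedures in the order below". The Visit 4 text says only "The site staff will perform/assess the following procedures", and Visit 3 has the same wording. The explicit timing rules are:
- SANDE, then symptom VAS, both before the AE review (8.1.1.1, 8.1.1.2);
- AE information before the other assessments (9.3.1);
- FCS after Drop Discomfort (8.1.1.3);
- STT at least 1 hour after IP and 20 minutes after FCS (8.1.1.4).

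None of them mentions dispensing or carton return. The listed order is therefore permitted but not required, and a site could dispense last without deviating.

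**The plan's own figure, as a check only.** n per group = 2 × (1.960 + 1.282)² × (20/15)² = 37.4, rounded up to 38; and 76/(1 - 0.15) = 89.4, rounded up to 90. Both agree with Protocol 10.2. Nothing here depends on them.

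**Illustration of what a grader shift would do.** Neither the FCS SD nor any shift is given in the documents; both are assumed. With no true difference, 45 per arm (Protocol 5.1) and an average shift b between arms, a two-sided 5% two-sample t-test has noncentrality b / (SD × √(2/45)) = b / (0.2108 × SD) on 88 degrees of freedom.

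| Assumed shift b | SD 2.0 | SD 2.5 | SD 3.0 |
|---|---|---|---|
| 0.5 point: noncentrality | 1.19 | 0.95 | 0.79 |
| 0.5 point: chance of p < 0.05 | 21.6% | 15.5% | 12.2% |
| 0.25 point: noncentrality | 0.59 | 0.47 | 0.40 |
| 0.25 point: chance of p < 0.05 | 9.0% | 7.6% | 6.8% |

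The planned analysis is an ANCOVA with site and baseline (SAP 7.6.1), so the t-test is an approximation.

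**The case against.** The strongest reply is that the lists at Visits 3-5 are checklists. They are not strictly chronological: the evening phone contact appears before the in-clinic reminder about the next morning's dose. This stands, and it limits the point to a permitted exposure. It does not remove the point, because sites are likely to work down the list and no other rule moves these two steps.

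Second, the plan has safeguards. Protocol 6.2 says subjects will not see the assignment on Days 2-28, with a caveat only for prior Restasis users, and Protocol 5.3 excludes prior use beyond 1 month. The coordinator alone handles IP and answers questions about it. Protocol 6.3 makes accidental unmasking a reportable deviation and lets a Sub-Investigator take over assessments. These help in part. But a subject who cannot name the product can still show or describe it to a grader who can, and the 6.3 provision acts only after unmasking has happened and been noticed.

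Third, the route to the grader is inferred. The outer carton is not described, so whether staff would see a difference is unknown. AE assessment is assigned to site staff without a masked label. STT is a ruler measurement with less room for judgement than staining. All of this stands.

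A reader might infer that every subject carries identifiable product into the masked assessments, that Schirmer testing is exposed at both visits, or that slit-lamp and end-of-treatment signs are compromised. The documents do not support this. The order is not mandated and there is no STT at Visit 3. At Visit 5 the carton is returned before slit-lamp, FCS and STT, and nothing is dispensed. Nor is Investigator masking the only masking left: Protocol 6.1 also keeps the Sponsor, CRO teams and other study personnel masked.

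**Conclusion.** The point holds as an avoidable weakness in Investigator masking, limited to FCS at Visits 3 and 4, STT at Visit 4 (less judgement-dependent) and the first AE review at Visits 3-5. It rests on four facts: the listed order, the visible difference between products, the absence of any described concealment by the outer carton, and the absence from the readable text of an instruction to subjects about showing or describing IP.

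The primary endpoint is untouched. It is subject-rated after Dose 1 at Visit 2, under double masking, and dispensing is listed after that rating.

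The size of any bias cannot be derived from the documents. The 12-22% and 7-9% figures show sensitivity to assumed shifts of 0.5 and 0.25 point and assumed SDs of 2.0-3.0. An average shift of 0.5 point would need widespread unmasking and a consistent direction of bias, and nothing in the plan shows that to be likely. This is a cheap improvement in conduct, and it does not invalidate the trial.

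**What to change.** - In Protocol 8.2.2.2, 8.2.2.3 and 8.2.2.4, have the unmasked coordinator collect the returned carton on arrival, before the subject meets masked staff.
- In 8.2.2.2 and 8.2.2.3, move dispensing to after the last masked assessment: FCS at Visit 3, STT at Visit 4.
- State that these two positions are binding, whatever the status of the rest of the list.
- At Visit 2 (after Dose 1) and at each later treatment visit, have the coordinator remind subjects not to show or describe the product or its storage to masked staff.

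None of this conflicts with the timing rules for SANDE, symptom VAS, AE review, FCS or STT. It needs no new staff or procedure and leaves the sample size unchanged. The cost is that the coordinator must see the subject at both the start and the end of Visits 3 and 4, and on arrival as well as for dosing at Visit 5.
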